BACKGROUND AND RATIONALE	4
AIM OF THE STUDY	5
METHODS	6
• STUDY DESIGN	6
• PATIENT ENROLLMENT	6
• OUTCOMES	6
1. primary	
2. secondary	
3. safety	
• PROCEDURES	8
STATISTICAL PLAN	9
STUDY TIMELINE	9
SUPPORT	10
ETHICAL AND DATA CONSIDERATIONS	10
REFERENCES	13

BACKGROUND AND RATIONALE

Ulcerative colitis (UC) is a chronic inflammatory bowel disease (IBD) affecting the colon and rectum. Despite the availability of multiple therapeutic options for patients with UC, achieving short-

term and long-term disease control remains challenging, and symptoms negatively impact on patients' quality of life (QOL) (1,2). Indeed, approximately two-thirds of patients fail to obtain or maintain remission after 1 year even with the use of current biologics agents. Janus kinase (JAK) pathways regulate immune signaling and are implicated in IBD pathogenesis (3). Upadacitinib (UPA) is an oral, selective, small molecule JAK inhibitor engineered to have preferential inhibitory effects for JAK1 that has recently received approval in Italy for the treatment of UC. UPA selectivity might allow the evaluation of higher doses, potentially providing greater efficacy without increasing some of the reported safety issues associated with JAK2 and JAK3 inhibition. The efficacy of UPA is supported by phase 2 (4) and phase 3 (5) explanatory trial.

In a phase 2 (4) dose-ranging, placebo-controlled induction study, patients with moderately to severely active ulcerative colitis received UPA at the following doses: 7,5 mg, 15 mg, 30 mg, and 45 mg once daily. UPA 45 mg once daily showed an optimal benefit–risk profile with the highest efficacy rates and no clinically relevant increase in safety events compared with lower doses and was therefore selected for the phase 3 induction dose. Considering a potentially more favorable long-term safety profile, two doses (15 mg and 30 mg once daily) lower than the induction dose were selected as the phase 3 maintenance doses; both doses also showed superior efficacy versus placebo in the phase 2b study.

In the induction analysis of a phase 3 trial (5), the primary endpoint, clinical remission at week 8, was achieved by 26-33% of patients receiving UPA versus 4-5% of patients receiving placebo (both $p < 0,0001$).

Moreover, in the maintenance analysis of the same trial, the primary endpoint defined as clinical remission at week 52, was achieved by 42% of patients receiving UPA 15 mg once daily, and 52% patients receiving UPA 30 mg once daily, and 12% of patients receiving placebo ($p < 0,0001$).

At present, the efficacy and safety data of UPA come mostly from clinical trials. Few real-world experiences (6,7) are available in the literature and one report is a multicenter case series from our center that is planned to be presented during the upcoming XIV IGIBD national congress. As stated in drug data sheet (8), UPA is indicated in the treatment of adult patients with moderate to severe active ulcerative colitis (evaluated with Mayo Score – disease activity index (9)) who have had an inadequate response, have lost the response or are intolerant to conventional therapy or a

biological agent. UPA is available in three doses 45,30 and 15 mg. Patients receive 45 mg orally every day for 8 or 16 weeks (depending on clinical judgment and according to risk-benefit evaluation) as induction therapy. At the end of induction period, patients in clinical remission will receive UPA 15mg or 30mg (depending on clinical judgment and according to risk-benefit evaluation) every day as maintenance therapy.

According to reported adverse events in both registrative trials (4,5), serious adverse events and adverse events leading to discontinuation of treatment were less frequent in the UPA 45 mg group than in the placebo group (serious adverse events 3% vs 5-6%; adverse events leading to discontinuation 2% vs 5-9%).

The most frequently reported adverse events in the maintenance part of the trial were nasopharyngitis (12-15%), creatine phosphokinase elevation (5-6%), arthralgia (6-10%) and upper respiratory tract infection (4-6%). Events of cancer, adjudicated major adverse cardiac events, or venous thromboembolism were reported infrequently. There were no treatment-related deaths.

Despite the drug presents an adequate safety profile, careful analysis of indications and contraindications must therefore be carried out by medical personnel before starting the drug.

AIM OF THE STUDY

The usefulness of real-life studies is already well clarified. A real-life multicenter study is therefore essential to assess the effectiveness and safety of this drug in our daily clinical practice outside the context of clinical trials. With our prospective observational study, the first in Italy on UPA in ulcerative colitis, we expect to obtain important observations on the efficacy of this novel therapeutic. By also collecting the adverse effects, a better definition of its safety profile is desirable.

METHODS

1. STUDY DESIGN

This is a 12-month observational, multicenter, prospective study. A retrospective part is planned to include patients who have already started the treatment from the EMA approval in March 2023. In detail, the planned study design involves an enrollment phase of about 6 months and then a prospective observational period of about 12 months during which clinical, biochemical, endoscopic, and histological information will be recorded. The number of patients included in the prospective enrollment phase will then be added to the number of patients retrospectively included already on therapy since 01.03.2023. In accordance with this, for patients retrospectively included and therefore already on UPA therapy, clinical and biochemical data will be retrospectively retrieved.

2.PATIENT ENROLLMENT

Inclusion criteria: patients with established diagnosis of UC according to standard criteria (10) aged ≥ 18 years receiving UPA for moderately to severely active UC, either experienced or naïve to any advanced therapies (biologics and/or small molecule) currently available will be enrolled. These inclusion criteria are equally applied for the retrospective part of the study as stated before.

Exclusion criteria: patients unwilling or unable to give informed consent to the study. Patients meeting criteria (11) for acute severe ulcerative colitis (ASUC) will also be excluded.

3.OUTCOMES

a. PRIMARY OUTCOME

The effectiveness of UPA in patients with ulcerative colitis is evaluated in terms of clinical remission at week 8 (t1), 26 (t3), and 52 (t4) defined as a partial mayo score (PMS) ≤ 2 .

b. SECONDARY OUTCOMES

As secondary outcomes, our study will evaluate:

- Clinical response at week 8 (t1), 16 (t2), 26 (t3), 52 (t4) defined as a decrease in PMS of ≥ 3 points and $\geq 30\%$ from baseline, plus either a decrease in the rectal bleeding sub score of ≥ 1 point or an absolute rectal bleeding sub score of 0 or 1.

- Steroid-free clinical remission at t4 defined as remission without the need of any kind of systemic steroids
- Biochemical remission at t3 and t4 defined as C-reactive protein < 0.5 mg/dl and fecal calprotectin level < 250 ug/g
- Endoscopic remission at t4 defined as Mayo endoscopic sub score (MES) ≤ 1 (12)
- Histological remission at t4 defined as a Nancy index ≤ 1 (13)
- Treatment persistency at t4 defined as percentage of patients continuing UPA as maintenance treatment through week 52

c. SAFETY OUTCOMES

Another aspect that will be assessed is the safety profile of the drug during all the period in terms of

- Any adverse events
- Serious adverse events are defined as any adverse reaction that results in death, is life-threatening, requires hospitalization or prolongation of existing hospitalization, results in persistent disability according to European Medicines Agency definition. There will be a focus on opportunistic Infections (principally Herpes Zoster infections), thrombo-embolic events and major adverse cardiovascular events (MACE)

Since the reporting of adverse events is the responsibility of the prescribing physician of the drug, it will be necessary for the investigating physician of each participating center to provide the report to AIFA.

4.PROCEDURES

To evaluate these outcomes, as previously described, the study involves 5 main evaluation points that are normally part of our clinical practice (see also Flow-Chart file):

T0 (baseline visit): at the beginning of the induction period of UPA treatment, general information regarding the disease will be collected.

T1 (8 weeks): clinical status will be re-evaluated with a telephone consultation and/or clinical examination if an objective examination is needed. At this time, as reported in the drug data sheet, the need for continued induction therapy and drug dosing will be assessed.

T2 (16 weeks): clinical status will be re-evaluated with a telephone consultation and/or clinical examination if an objective examination is needed. At this time, as reported in the drug data sheet, drug dosing will be assessed.

T3 (26 weeks): the clinical status will be re-evaluated with a telephone consultation and/or clinical examination if an objective examination is needed. At this time, as reported in the drug data sheet, drug dosing will be assessed. In addition to the previous evaluation, a C-reactive protein blood sample and fecal collection will be requested for a calprotectin assay.

T4 (52 weeks): the clinical status will be re-evaluated with a telephone consultation and/or clinical examination if an objective examination is needed. At this time, as reported in the drug data sheet, drug dosing will be assessed. A C-reactive protein blood sample and fecal collection will be requested for a calprotectin assay. If possible, a colonoscopy with biopsy sampling will be requested.

STATISTICAL PLAN

We estimate a sample size with normal distribution. According to the available literature, about 250 patients are planned to be enrolled.

Continuous variables are expressed as mean \pm standard deviation (SD) and categorical variables are summarized as frequency and percentage. The Chi-square, or Fisher's exact test when

appropriate, and the independent samples T-test are applied for categorical and continuous variables respectively.

The effectiveness of UPA by clinical remission in the two groups (Partial mayo score (PMS) <2 vs PMS >2) is calculated by Chi-square or Fisher's exact test at week 8 (T1), week 16 (T2), week 26 (T3), week 52 (T4).

Another comparison in primary and secondary outcomes is performed by T Student Test (or One Way ANOVA Test with Post Hoc Multiple Comparison LSD Method) in groups of different type of patients (by gender, by range age).

The influence of risk factors on the outcomes is analyzed by multivariate binary logistic regression with Backward Wald method analysis for the effectiveness of UPA rate and with Linear Regression multivariate analysis with Backward method for week 8 (T1), week 16 (T2), week 26 (T3), week 52 (T4). P <0.05 is considered statistically significant.

STUDY TIMELINE

Project start date: 01.12.2023 (and in any case not before approval of the study by the EC)

Completion date of patients' enrollment: 01.06.2024

Data collection completion date: 01.06.2025

Data analysis: after data collection completion 01.07.2025

SUPPORT

IGIBD represents the sponsor for this study. Although there is no direct financial support, IGIBD provides the expertise of a clinical manager and a statistician for data analysis.

ETHICAL AND DATA CONSIDERATIONS

1.ETHICAL COMMITTEE

All participating centers will need Ethical Committee's approval before starting with the patients' enrollment.

2.PATIENT PROTECTION

The study coordinator ensures that this study is conducted in accordance with the Helsinki Declaration (amendments of Tokyo, Venice, Hong Kong, Somerset West, Edinburgh, Washington, Tokyo and Seoul) or with Italian laws and regulations.

The protocol was written, and the study will be conducted in accordance with the ICH guidelines for good clinical practice.

The protocol and its annexes are subject to review and approval of the Independent Ethical Committee of competence and each participating center must obtain the approval of the Ethics Committee of its institute.

3.SUBJECT IDENTIFICATION – PERSONAL DATA PROTECTION

All records identifying the subject must remain confidential and, with the limits permitted by applicable laws, are not made available to the public. The patient's name will not be requested or registered by the Data Center. A sequential identified number will be automatically assigned to each patient registered in the study. Patient information or documentation should be considered "anonymous", and as such not subject to privacy laws, only when a "key" that allows patient identification is no longer available.

4.PROCEDURES FOR COLLECTING DATA

All data required by the study will be recorded in a REDCap database. REDCap is a platform residing on a remote server where the anonymized data will be stored.

Each authorized user can access the database via the web with a dedicated username and password. Each center will see and can modify only its cases, while the principal investigator will be able only to see, data entered by each Center. Every access to REDCap is monitored by the system, as well as every variation of the data contained. Patients will be pseudo-anonymized and

identification data will not be included. It will be the principal investigator's responsibility to keep separately a file containing the patient's personal data (and folder number) together with the code assigned by REDCap for subsequent data quality checks.

5.CONFLICT OF INTEREST

Any investigator and/or research staff member who has a conflict of interest with this study (such as patent ownership, royalties, or financial gain greater than the minimum allowable by their institution) must fully disclose the nature of the conflict of interest.

6.DATA SHARING POLICY

The results of this study will be published and/or presented at scientific meetings. Any formal publication of study results will be a collaborative effort between all the Investigators. All manuscripts or abstracts will be reviewed and approved in writing by the Principal Investigator prior to submission. A final integrated clinical/statistical report will be prepared at the end of the study. The papers produced will respect individual participants whose data are shared and will follow the authorship policy of journal. The order in which the authors will be listed in the subtitle will depend on the number of patients enrolled, except for the first 4 names and last name that will be attributed by the Steering Committee. If the number of authors is more than that allowed by the data sharing policy of the journal, the remaining authors will be included inside the term "working group" at the end of the manuscript, so that all investigators/authors will be in any case identified on PubMed. In signing the protocol/protocol amendment(s), every participating Investigator agrees to keep all information and results concerning the study confidential. The confidentiality obligation applies to all personnel involved at each site. Information about study subjects will be kept confidential and managed under the applicable laws and regulations. The data collection system for this study uses built-in security features to encrypt all data for transmission in both directions, preventing unauthorized access to confidential participant information. Access to the system will be controlled by a sequence of individually assigned user identification codes and passwords, made available only to authorized personnel who have completed prerequisite training.

REFERENCES

1. Ungaro R et al. Ulcerative colitis. Lancet 2017
2. Rubin DT et al. ACG clinical guideline: ulcerative colitis in adults. Am J Gastroenterol 2019
3. Boland BS et al Update on Janus kinase antagonists in inflammatory bowel disease. Gastroenterol Clin North Am 2014
4. Sandborn W et al. Efficacy of Upadacitinib in a RCT of patients with active ulcerative colitis. Gastroenterology 2020

5. Danese S et al. Upadacitinib as induction and maintenance therapy for moderately to severely active ulcerative colitis: results from three phase multicenter, double-blind, randomized trials. *The Lancet* 2022

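### Treatment persistency is set as a week-52 percentage and no time-to-event method is named, so the analysis as written uses neither stop times nor the partial follow-up of patients lost while on upadacitinib

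*Protocol*

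**What the plan says.** The Protocol (Methods, 3. Outcomes, b. Secondary outcomes) gives the last of six secondary outcomes as "Treatment persistency at t4 defined as percentage of patients continuing UPA as maintenance treatment through week 52". This is a yes/no status at one time point.

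The Statistical Plan says that "categorical variables are summarized as frequency and percentage". The tests it names are chi-square or Fisher's exact, the t-test and one-way ANOVA. The models are "multivariate binary logistic regression with Backward Wald method analysis" and linear regression. No Kaplan-Meier, log-rank or Cox analysis appears. The planned size is given as "about 250 patients are planned to be enrolled".

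The Study Design section describes "an enrollment phase of about 6 months and then a prospective observational period of about 12 months" and adds patients who began upadacitinib from March 2023 onward, whose earlier data are collected retrospectively. Under Procedures, status is assessed at weeks 8, 16, 26 and 52, by telephone, by examination or both.

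The protocol states no expected loss to follow-up, no expected persistency and no rule for a patient whose week-52 status is unknown.

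**The concern.** Persistency is in substance time on drug. No contact is listed between weeks 26 and 52, so a patient on upadacitinib at week 26 who misses the last contact has no week-52 status. A simple percentage must count that patient as stopped, count the patient as continuing, or leave the patient out. Each choice gives a different answer, and none uses the 26 weeks of treatment that were observed.

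Two things are at stake. One definition can yield results that differ by about as much as the sampling error. And one week-52 figure does not show whether patients stop during the 8- or 16-week induction or during maintenance.

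Two features of the design bear on the same estimate:

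- **Denominator.** The reference to maintenance treatment leaves open whether the base is all starters or only those who reached maintenance.
- **Retrospective patients.** The Study Design section describes them as already on therapy. If being on drug was in effect a condition of inclusion, early stoppers are under-represented and persistency is pushed upward.

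**Working it through.** **Inputs from the Protocol.** n is about 250 (Statistical Plan). The Study Timeline gives completion of "enrollment: 01.06.2024" and "Data collection completion date: 01.06.2025". That is 365 days against 52 × 7 = 364, so a patient who starts treatment by the close of enrolment can just reach week 52. Little administrative censoring is expected; the issue is loss.

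**Plan's own figure.** There is none to reproduce. No persistency rate, loss rate or precision target is stated, and n serves here only for the half-width.

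**Assumptions.** True week-52 persistency S is 60%, 70% or 80%. The cumulative probability of loss by week 52, L, is 5%, 10% or 15% in the absence of stopping. Hazards are constant and loss is independent of stopping.

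**Formulas.** With time in units of 52 weeks:

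- stop hazard h = −ln S; loss hazard c = −ln(1 − L)
- seen to continue: K = S(1 − L)
- seen to stop: D = h/(h + c) × (1 − K)
- lost while on drug: 1 − K − D
- lost counted as stopped: K
- lost dropped: K/(K + D)
- Kaplan-Meier target under independent loss: S
- 95% half-width: 1.96 × √(S(1 − S)/250)

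**Worked case, S = 70%, L = 10%.**

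- h = 0.3567 and c = 0.1054
- K = 0.70 × 0.90 = 0.630
- D = 0.3567/0.4620 × 0.370 = 0.286
- Lost while on drug = 1 − 0.630 − 0.286 = 0.084
- Counted as stopped: 63.0%, which is 7.0 points low
- Dropped: 0.630/0.916 = 68.8%, which is 1.2 points low
- Half-width: 1.96 × √(0.21/250) = 5.7 points

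The two simple readings differ by 68.8 − 63.0 = 5.8 points, about one half-width. A simulation of 2,000,000 patients gave 63.0% and 68.8%.

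**Range.** Each cell gives the estimate and its error in points.

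| S (half-width) | L | Lost = stopped | Lost dropped |
|---|---|---|---|
| 60% (6.1) | 5% | 57.0% (−3.0) | 59.3% (−0.7) |
| 60% | 10% | 54.0% (−6.0) | 58.6% (−1.4) |
| 60% | 15% | 51.0% (−9.0) | 57.8% (−2.2) |
| 70% (5.7) | 5% | 66.5% (−3.5) | 69.4% (−0.6) |
| 70% | 10% | 63.0% (−7.0) | 68.8% (−1.2) |
| 70% | 15% | 59.5% (−10.5) | 68.1% (−1.9) |
| 80% (5.0) | 5% | 76.0% (−4.0) | 79.6% (−0.4) |
| 80% | 10% | 72.0% (−8.0) | 79.1% (−0.9) |
| 80% | 15% | 68.0% (−12.0) | 78.6% (−1.4) |

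With no loss, the simple percentage and Kaplan-Meier agree.

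**If loss is not independent.** Suppose every lost patient had in fact stopped when lost. In the worked case the true value is then 63.0%, counting losses as stops is right, and Kaplan-Meier, at 70%, is 7 points too high.

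**The case against.** The strongest objection is that the protocol adopts neither of the two rules behind these errors. Handling of losses and censoring is commonly left to the statistical analysis plan, which is not at hand. A percentage continuing through week 52 can also be read off a Kaplan-Meier curve, so the outcome definition alone does not force a crude estimator. This stands. A reader might infer that every lost patient will be counted as a stopper or dropped, and that the result will therefore be biased; the text does not say so. What remains is narrower: the protocol sets out its own list of methods, and none of them uses time on drug.

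Three other tempting readings are also unsupported:

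- **That stop dates are discarded.** No named analysis uses them, but the protocol does not say that they go uncollected, and dosing is reviewed at every contact.
- **That persistency is a headline outcome.** It is one of six secondary outcomes.
- **That it is the outcome most exposed to loss.** Drug status can be learned by telephone, while biochemical remission needs samples and the week-52 colonoscopy is requested only if possible.

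The size also depends on the rule. At 5% loss, or if lost patients are dropped, the error lies inside the sampling half-width throughout the range examined.

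Finally, Kaplan-Meier is no cure by itself. It relies on independent loss, and without delayed entry it would not correct for missing early stoppers among retrospective patients. Both limits are accepted and shape the fix.

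**Conclusion.** The concern holds in a limited form. Persistency is set as a week-52 percentage, and every method named is binary or continuous, so the analysis as written leaves stop times and partial follow-up unused.

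Under constant hazards, independent loss of 5-15% and true persistency of 60-80%, a simple percentage is 3 to 12 points low if losses count as stops and 0.4 to 2.2 points low if they are dropped. The half-width is about 5 to 6 points at n = 250. The loss and persistency rates are assumptions, because the protocol gives none. Selection of retrospective patients still on drug would act in the opposite direction, by an amount that the document does not allow to be estimated.

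This is a worthwhile, cheap improvement to a secondary outcome. It does not show that the planned result will be biased.

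**What to change.** 1. Analyse persistency as time from first upadacitinib dose to permanent stop, and state that the denominator is all starters.
2. Report the Kaplan-Meier estimate with 95% CI at weeks 8, 16, 26 and 52. Censor at last contact patients lost while on drug.
3. For retrospective patients included only because they were still on drug, use delayed entry: they join the risk set at their inclusion date. Retrospective patients identified from all starters, whether or not they had stopped, enter at first dose. The protocol should say which applies.
4. Report the percentage with lost patients counted as stopped as a sensitivity analysis. It is a lower bound with respect to loss, and it matters because Kaplan-Meier overstates persistency if loss signals stopping. It does not address the selection of retrospective patients, which item 3 covers.

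The cost is a few sentences, one standard curve, and the start, stop, inclusion and last-contact dates in the database. The price in assumptions is independent censoring, which item 4 puts to the test.

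### Week-52 persistency is biased upward because retrospective patients qualify by still being on UPA when included

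*Protocol*

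**What the plan says.** All references are to the Protocol.

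- **Outcome** (Methods, 3. Outcomes, b. Secondary outcomes): "Treatment persistency at t4 defined as percentage of patients continuing UPA as maintenance treatment through week 52". Nothing is said there about patients who enter after some time on the drug.
- **Who enters the retrospective part** (Methods, 1. Study design): the opening description is "A retrospective part is planned to include patients who have already started the treatment from the EMA approval in March 2023". Later sentences in the same section are narrower. The prospective number is "added to the number of patients retrospectively included already on therapy since 01.03.2023", and "for patients retrospectively included and therefore already on UPA therapy, clinical and biochemical data will be retrospectively retrieved".
- **Formal criterion** (Methods, 2. Patient enrollment): adults with UC "receiving UPA for moderately to severely active UC", followed by "These inclusion criteria are equally applied for the retrospective part of the study as stated before".
- **Time origin** (Methods, 4. Procedures): T0 is the start of UPA induction, not the date of inclusion.
- **Dates** (Study timeline): project start 01.12.2023; "Completion date of patients' enrollment: 01.06.2024".
- **Analysis** (Statistical plan): about 250 patients, with no split or cap between the two parts. Categorical variables are summarised as frequency and percentage.

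**The concern.** Under the formal criterion, a retrospective patient must be receiving UPA at inclusion, yet week 52 is counted from the start of induction. Such a patient has by definition stayed on the drug from T0 to inclusion. Anyone who began in the same weeks and stopped for non-response or an adverse event is not in the database. This is left truncation (prevalent-user selection), and a simple percentage makes no allowance for it.

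Persistency is the only outcome in the Protocol that directly measures staying on the drug, and the stated aim is effectiveness and safety in daily practice, where early stopping is central. Missing early stoppers can only raise the figure. The error grows with the retrospective share, which is not limited, and does not shrink with more patients. The same rule also thins early stoppers from the week-8 and week-26 remission rates; that effect is not quantified here.

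**Working it through.** The Protocol gives no expected persistency and no derivation of the 250, so there is no planned figure to reproduce. The check has two parts: how much time on drug retrospective patients bring with them, and what that does to the rate.

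**Step 1. Time on UPA at inclusion (Protocol dates).**
- 01.03.2023 to 01.12.2023: 275 days / 7 = 39.3 weeks.
- 01.03.2023 to 01.06.2024: 458 days / 7 = 65.4 weeks.

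A retrospective patient can have up to 39 weeks on drug at project start and up to 65 weeks at the close of enrolment. Anyone with 52 weeks or more at inclusion has met the outcome before entering.

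**Step 2. Model (assumptions).** Let p be the true week-52 persistency, with values 60%, 70% and 80%. The stopping rate is constant, so S(t) = p^(t/52). Starts are even over 01.03.2023 to 01.12.2023, and all retrospective patients are included on 01.12.2023, so time on drug A is uniform on 0 to 39.3 weeks.

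- Share of starters still on UPA at inclusion: m = mean of S(A) = (1 − p^(39.3/52)) / (−ln p × 39.3/52).
- Persistency observed in retrospective patients: p / m.
- Pooled error: f × (p/m − p), where f is the retrospective share of included patients. Prospective patients enter at T0 and are taken as unbiased.

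| True p | m | Retrospective reads | Error, retrospective | Pooled error, f = 30 / 50 / 70% |
|---|---|---|---|---|
| 60% | 0.830 | 0.60/0.830 = 72.3% | 12.3 points | 3.7 / 6.2 / 8.6 |
| 70% | 0.877 | 0.70/0.877 = 79.9% | 9.9 points | 3.0 / 4.9 / 6.9 |
| 80% | 0.920 | 0.80/0.920 = 86.9% | 6.9 points | 2.1 / 3.5 / 4.9 |

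**Step 3. Sensitivity to the assumptions.**
- *Earlier stopping.* With half of all stops spread evenly over weeks 0 to 16 and the rest over weeks 16 to 52, the pooled error at f = 30 / 50 / 70% is 4.4 / 7.4 / 10.3 points for p = 60% and 2.6 / 4.4 / 6.1 points for p = 80%.
- *Later inclusion.* If the same starters are all included on 01.06.2024 (constant stopping rate, S held at its week-52 value beyond 52 weeks), true rates of 60 / 70 / 80% read 92 / 94 / 96% in retrospective patients. At f = 50% the pooled figures are 76 / 82 / 88%.
- *Later-weighted starts.* For p = 70%, f = 50% and inclusion on 01.12.2023, starts rising linearly over the 39.3 weeks give a pooled error of 3.2 points. Starts confined to the last 17 weeks give 2.1 points. Even starts give 4.9.

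**Step 4. Comparison with sampling error.** The 95% half-width is 1.96 × √(p(1−p)/250), which is 6.1, 5.7 and 5.0 points for p = 60%, 70% and 80%. The bias ranges from well under half of this to more than all of it.

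**The case against.** The strongest reply is that the Protocol does not clearly exclude stoppers. The sentence that sets up the retrospective part speaks of patients who have started treatment, which a stopper satisfies. Neither exclusion criterion mentions discontinuation. The words on receiving UPA for active disease could describe the indication at T0, since a patient in remission on maintenance no longer has moderately to severely active disease. On that view the defect is loose wording. This has some force, but the formal criterion is in the present tense and is carried over to the retrospective part, and two further statements describe these patients as already on therapy, one of them as a consequence of being included retrospectively. Centres recruit by the criterion as written. If all starters were intended, the text still needs changing.

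A second reply is that analysis sets and delayed entry belong in an analysis plan, which is not shown. It is true that reporting prospective starters alone, or using delayed entry, would help without changing eligibility. But eligibility is fixed in the Protocol, and a rule on the denominator cannot bring back patients who were never enrolled.

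Third, the size rests on inputs the Protocol does not give, and a later-weighted start pattern lowers it to 2 or 3 points in the case worked above, below the sampling half-width. That stands: the direction is certain under this reading, the size is not. The 65-week figure is also an extreme, needing a March 2023 starter included on the last enrolment day.

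Fourth, the mention of maintenance in the definition may limit the denominator to patients who reached maintenance. Stops during induction would then matter less, but retrospective patients who stopped during maintenance before inclusion would still be missing.

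Finally, this is one of six secondary outcomes with no hypothesis attached, which limits the consequence.

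**Conclusion.** The concern holds. Applied as written, the eligibility rule leaves out retrospective-period starters who stopped before inclusion, and the pooled week-52 percentage is biased upward. With inclusion at project start, even starts and a constant stopping rate, the pooled error is about 2 to 9 points for true persistency of 60% to 80% and a retrospective share of 30% to 70%. It is about 3 to 10 points if half of stops fall by week 16, and more if inclusion is later. The true rate, the retrospective share, the start pattern and the stopping pattern are all assumptions. The upward direction does not depend on the values chosen for them, but it does depend on reading the inclusion criterion as requiring current treatment, which is what the text says in three places against one looser sentence. The change should be made, although it concerns a secondary outcome.

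**What to change.** **Preferred.** For the retrospective part, replace the requirement to be receiving UPA with: every patient at the centre who took a first dose of UPA for moderately to severely active UC from 01.03.2023, whether or not still taking it at inclusion. Identify them from a consecutive list drawn from prescription records, and count those who stopped as non-persistent. Define persistency as the percentage, of all patients who started UPA, still taking it at any dose at week 52.

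**If stoppers cannot be included.** Report persistency in prospectively enrolled starters as the main figure. Analyse the retrospective patients by time on drug with delayed entry: Kaplan-Meier from T0, with each patient at risk only from the inclusion date. Record that date for every patient.

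**Cost.** The preferred route needs one reworded criterion, a list of starters per centre, and consent from patients who have stopped. The reported rate will probably be lower. The fallback costs precision: if the prospective patients number 125 (an assumption), the 95% half-width at 70% is 1.96 × √(0.70 × 0.30/125) = 8.0 points, against 5.7 at 250.
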